3.0 Secondary Analyses

All secondary analyses will be performed separately for each of the two primary cohorts. The analyses below will follow the guidelines outlined in section 2.2. Secondary analyses will be considered significant if the p-value is less than 0.01.

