3.2 Best Distance Visual Acuity at 36-Months

A treatment group comparison of the best distance visual acuity (logMAR) in the better-seeing eyes at 36 months post-randomization will be performed using analysis of covariance (ANCOVA) models. A similar analysis will be performed to compare visual acuity in the worse-seeing eye between treatment groups. Both analyses will adjust for age at the 36-month exam and visual acuity in the eye at enrollment.

Best distance visual acuity in each eye is defined as the minimum logMAR visual acuity between measurements reported with and without trial frames, during initial assessment and retest, if required. If no retest is required at 36 months, best visual acuity is the minimum of logMAR visual acuities reported with trial frames and without trial frames during the initial assessment. If a retest is required at 36 months, best visual acuity is the minimum of logMAR visual acuities reported with and without trial frames, during the initial assessment and retest at 36 months. If a 37-month visit is required, best visual acuity is the minimum of logMAR visual acuities reported during initial assessment and retest without trial frames at the 36 months and during initial assessment with trial frames at the 37 months, if no retest is required at 37 months. If a retest is required at 37 months, best distance visual acuity is the minimum of logMAR visual acuities reported during initial assessment and retest without trial frames at 36 months and initial assessment and retest with trial frames at 37 months.

The better-seeing eye at 3 years will be defined as the eye with the smaller best logMAR visual acuity at 3 years.

For the purposes of this analysis, a value of 1.7 will be assigned to eyes that have a visual acuity worse than 20/800.

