4.3 Change in Refractive Error from Baseline to Outcome

An analysis of covariance model will be used to compare the change in spherical equivalent (SE) refractive error in the eye that was more hyperopic at baseline from baseline to 36 months between treatment groups. The model will adjust for SE refractive error at baseline. The analysis will be repeated for the eye classified as less hyperopic at baseline.

If the change in refractive error differs at 36 months, an analysis of covariance model will be used to evaluate whether the relationship between the relationship between age at baseline and change in refraction from baseline to 36 months in the more hyperopic eye differs by treatment group. The model will include age at baseline, treatment group, and an interaction between age at baseline and treatment group. Analyses will be repeated to evaluate whether the relationship between age at baseline and change in refractive error from baseline to 36 months in the less hyperopic eye differs by treatment group.

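### Section 3.2 adjusts for the enrollment acuity of an eye chosen by its 36-month result, which biases the better-eye and worse-eye estimates slightly when treatment affects the two eyes unequally (minor)

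*SAP*

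**What the plan says.** SAP section 3.2 plans "A treatment group comparison of the best distance visual acuity (logMAR) in the better-seeing eyes at 36 months post-randomization" by ANCOVA, and adds: "A similar analysis will be performed to compare visual acuity in the worse-seeing eye between treatment groups". The eye is chosen by the result: "The better-seeing eye at 3 years will be defined as the eye with the smaller best logMAR visual acuity at 3 years". The covariates are set in one sentence: "Both analyses will adjust for age at the 36-month exam and visual acuity in the eye at enrollment". The section does not say which eye is meant there. The natural reading is the eye whose 36-month acuity is being analysed, and nothing else in the SAP defines it otherwise.

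Section 3.0 has these analyses run separately in each age cohort and sets the threshold: "Secondary analyses will be considered significant if the p-value is less than 0.01". By contrast, section 4.3 analyses the change in spherical-equivalent "refractive error in the eye that was more hyperopic at baseline from baseline to 36 months", so there the eye is fixed before treatment.

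**The concern.** Baseline adjustment in a randomised trial is safe because the covariate cannot be influenced by treatment, so any difference between arms is chance and the model rightly removes it. In section 3.2 the choice of eye can be influenced by treatment. Suppose glasses help the initially worse eye more. That eye then ends as the better-seeing eye more often in the glasses arm, and the enrollment acuity entered in the better-eye model is on average poorer there. ANCOVA reads this as an unlucky baseline and credits the glasses arm for it. The worse-eye model does the reverse.

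At stake is the size of two reported secondary effects, and the power to detect an effect at the 0.01 threshold where the estimate is pulled towards zero. An effect that differs between eyes is conceivable in this trial: the failure criteria in section 2.1 and the amblyopia definition in section 4.1 both use interocular difference.

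**Working it through.** The SAP states no SD, correlation, effect size or sample size for this analysis, so there is no figure of the plan's to reproduce. The check is of the mechanism, and every input is an assumption.

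**Formula.** Let D_Y be the raw arm difference (glasses minus observation) in the selected eye's 36-month acuity, D_X the arm difference in that eye's enrollment acuity, and b the within-arm slope. Then

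ANCOVA estimate = D_Y − b × D_X.

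If the covariate is fixed before randomisation, D_X averages zero and the estimate targets D_Y. If treatment changes which eye is selected, D_X does not average zero, and the bias is −b × D_X.

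**Assumed inputs.** Two eyes per child; SD 0.10 logMAR; between-eye correlation 0.4, 0.6 or 0.8; enrollment-to-36-month correlation 0.3, 0.5 or 0.7; 1:1 allocation; 2,000,000 simulated children per scenario. Age is left out because it is not eye-specific. Negative values are benefit.

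**Worked case.** Correlation 0.5 over time and 0.6 between eyes; effect −0.10 on the enrollment-worse eye only.
- Better eye: D_Y = −0.0566, D_X = +0.0324, planned estimate −0.0702. Implied b = (0.0702 − 0.0566)/0.0324 = 0.42.
- Worse eye: D_Y = −0.0433, D_X = −0.0323. With b = 0.42, −0.0433 + 0.42 × 0.0323 = −0.0297, which is the simulated planned estimate.

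**Range, effect on the enrollment-worse eye only.**

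| Effect | Correlation over time / between eyes | Better eye: raw → planned | Worse eye: raw → planned | Bias (absolute) |
|---|---|---|---|---|
| −0.05 | 0.3 / 0.4 | −0.0246 → −0.0283 | −0.0251 → −0.0215 | 0.004 |
| −0.05 | 0.5 / 0.6 | −0.0225 → −0.0294 | −0.0273 → −0.0205 | 0.007 |
| −0.05 | 0.7 / 0.8 | −0.0217 → −0.0320 | −0.0285 → −0.0179 | 0.010–0.011 |
| −0.10 | 0.5 / 0.6 | −0.0566 → −0.0702 | −0.0433 → −0.0297 | 0.014 |
| −0.10 | 0.7 / 0.8 | −0.0602 → −0.0817 | −0.0399 → −0.0183 | 0.022 |

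**Other effect patterns.** These use a second model: slope 0.5, between-child SD 0.10, eye SD 0.06.
- Benefit of 0.05 in the enrollment-worse eye only: better eye −0.030 planned against −0.023 raw; worse eye −0.020 against −0.027. The bias is 0.007, and 0.007/0.023 is about 30%. Another residual structure gave 0.005 for the same case.
- Benefit of 0.03 in the enrollment-better and 0.05 in the enrollment-worse eye: −0.040 against −0.038, and −0.040 against −0.043. The bias is about 0.003, and 0.003/0.043 is about 7%.
- Benefit of 0.05 in the enrollment-better eye only: better eye −0.033 against −0.039. The direction reverses: the better-eye effect is understated and the worse-eye effect overstated.

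**No effect, or the same effect in both eyes.** Bias is 0.000. In 10,000 null trials at each of 100 and 200 children, rejection was 1.1–1.2% at the 0.01 level and 4.8–5.4% at the 0.05 level.

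**Check of the remedy.** With the same 36-month outcomes but enrollment-fixed covariates (the enrollment-better or enrollment-worse eye, or both), the estimate matched the raw randomised difference to within 0.0003 logMAR in every scenario.

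**The case against.** The strongest reply is that the bias needs an effect pattern the SAP never states. Glasses are prescribed for the child, not for one eye, and the anisometropia subgroups in section 3.7 stop at 1.50D, so a benefit confined to one eye is an extreme case. Under the milder 0.03/0.05 split the bias is about 0.003 logMAR, a small fraction of a 0.1 logMAR line. This stands, and it is why the point is minor.

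It can also be said that the covariate may have been meant as the better or worse eye as ranked at enrollment. That would leave no bias and only a wording problem. It is the less natural reading, but the text does not exclude it, and the same sentence needs changing either way.

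Four stronger inferences are tempting, and the SAP does not support them:
- *The covariate is a post-randomisation measurement.* It is not. The acuity is measured at enrollment; only the choice of eye comes later.
- *The glasses effect is always overstated in the better eye and understated in the worse eye.* That follows only if the enrollment-worse eye gains more. It reverses if the other eye does, and nothing moves if both gain equally.
- *The tests produce too many false positives.* They do not when treatment has no effect in either eye.
- *Section 4.3 shows that section 3.2 has the wrong endpoint.* Section 4.3 studies change over time and must follow one eye. The better and worse of two eyes at 36 months are legitimate child-level outcomes. The fault lies only in the covariate paired with them.

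**Conclusion.** The point holds as a minor one. On the natural reading of section 3.2, treatment can influence which eye's enrollment acuity enters the model. Unequal effects in the two eyes then bias the better-eye and worse-eye estimates by about equal amounts in opposite directions.

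Under middling assumptions the bias is about 0.003 to 0.007 logMAR for a 0.05 logMAR effect. At the highest correlations tried it is about 0.011 for that effect, and about 0.02 if a 0.10 effect is confined to one eye. All these figures rest on assumed SDs, correlations and effect patterns. Neither the size nor the direction in this trial can be read from the SAP.

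The problem is confined to the two acuity ANCOVAs of section 3.2 in each cohort. The primary failure comparison and the Barnard comparisons in sections 3.3, 3.4 and 3.6 do not use this covariate.

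**What to change.** Keep the 36-month better-eye and worse-eye outcomes. In section 3.2, replace the eye-specific enrollment covariate with two covariates fixed at enrollment and used in both models: the acuity of the eye that saw better at enrollment and the acuity of the eye that saw worse at enrollment. Age at the 36-month exam stays.

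Defining the outcome eye at baseline is not proposed. It would also remove the bias, but it estimates something else, namely the effect on a given eye.

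The cost is one sentence and a refit of four models (two eyes in two cohorts) on the same data. There is a small side benefit: section 3.2 gives no rule for children whose eyes tie at 36 months, so their present covariate is undefined, whereas enrollment-fixed covariates need no 36-month tie rule. Because the version history shows that results had been seen before version 3.0, the refit should be reported beside the planned model and labelled as a later change.

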3.3 Proportion of Subjects with Age-Normal Distance Visual Acuity at 36 Months

A treatment group comparison of the proportion of subjects meeting age-normal distance visual acuity in **both** eyes at 36 months will be performed using Barnard's exact test.

The best reported visual acuity (*see section 3.2*) in each eye will be used to identify subjects who meet age-normal distance visual acuity. Subjects will be classified as meeting age-normal distance visual acuity if the best reported visual acuity in both eyes are within age-normal range.

3.4 Presence of Strabismus at 36 Months

A treatment group comparison of the proportion of subjects who meet failure criteria for strabismus at 3 years, defined as having measureable heterotropia at distance, having measureable heterotropia at near, or having strabismus surgery prior to 3 years, will be performed using Barnard's exact test.

Once deterioration criteria are met, masked exams were waived for the remainder of the study, except for the 36 month exam. If a subject were to deteriorate due to poor stereoacuity or visual acuity, they would not be retested if measurable heterotropia was present at a subsequent exam. Hence it is not possible to determine whether strabismus failure criteria, which require a retest, were met at any subsequent exam other than the 36 month exam

3.5 Best Near Stereoacuity at 36 Months

A treatment group comparison of best stereoacuity (log arcseconds) will be performed using an ANCOVA model, adjusting for age at the 36-month examination and the magnitude of anisometropia (using the most recent cycloplegic refraction).

Best near stereoacuity is defined as the minimum stereoacuity between measurements reported with and without trial frames, during initial assessment and retest, if required. If no retest is required at 36 months, best stereoacuity is the smaller of the measurements reported with and without trial frames during the initial assessment. If a retest is required at 36 months, best near stereoacuity is the minimum of measurements reported with and without trial frames, during initial and retest at 36 months. If a 37-month visit is required, best near stereoacuity is the minimum of measurements reported for initial assessment and retest without trial frames at 36 months and the initial assessment at 37 months, if no retest is required at 37 months. If a retest is required at 37 months, best near stereoacuity is the minimum of measurements reported during initial assessment and retest without trial frames at 36 months and initial assessment and retest with trial frames at 37 months.

For the purposes of this analysis, a value of 1600 will be assigned to participants with no detectable stereoacuity (nil).

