1 **Hyperopia Treatment Study (HTS1)**
 2 **Immediate versus Delayed Treatment In Children with Moderate**
 3 **Hyperopia**

4
 5 **Statistical Analysis Plan**
 6 **Version 3.0**

7
 8
 9
 10 Statistical Analysis Plan Version: 3.0, 25Jul18
 11 Protocol Version: 3.0, 28Jan15

12
 13
 14 **VERSION HISTORY**

The following table outlines changes for the analysis plan:

VERSION NUMBER	AUTHOR	APPROVER	EFFECTIVE DATE	REVISION DESCRIPTION*
1.0	[name]	[name]	12-19-17	Initial draft written after study was completed but before manuscript was written.
2.0*	[name]	[name]	05-14-18	Lead authors decided to redefine “best” stereoacuity and visual acuity at the 3-year outcome visit to be consistent with what was done for the IXT study. When preparing to unmask the study investigators to the results, the leads realized that it was not our intent to compare deterioration rates between the two groups. In the planning phase, the planning committee felt the deterioration rates in each group would aid in interpreting the results. The committee felt a formal statistical comparison was not needed because the rate of deterioration was expected to be higher in the observation group than in the glasses group.
3.0*	[name]	[name]	07-27-18	Lead authors decided to redefine best stereoacuity and best visual acuity at the 3-year outcome visit as the best of measurements reported with and without trial frames, during the initial assessment and retest, if required. During their final review of the manuscript, the leads realized that results reported for primary and secondary analyses were discordant. The leads determined that the definitions of best stereoacuity and best visual acuity needed updating to reflect the study design and to be in concordance with results reported in the primary analysis.

* indicate in the description if the changes were made after review of outcome data

15 **1.0 Primary Objective**

16 The primary study objective is to compare visual outcomes and development of strabismus after a
17 36-month follow-up period in two age cohorts (children age 12 to <36 months and children age
18 36 to <72 months) with moderate hyperopia (spherical equivalent +3.00D to +6.00D in either
19 eye) who are prescribed glasses either immediately or only after pre-specified deterioration
20 criteria are met.

21
22 **2.0 Primary Analysis**

23 The primary analysis will be a treatment group comparison of the proportion meeting failure

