3.6 Proportion of Subjects with Age-Normal Stereoacuity at 36-Months

A treatment group comparison of the proportion of subjects meeting age-normal near stereoacuity at 36 months will be performed using Barnard's exact test.

Subjects are considered to have age-normal stereoacuity if their best reported near stereoacuity (*see section 3.5*) is within age-normal range.

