3.7 Subgroup Analysis

In accordance with NIH guidelines, a subgroup analysis of treatment effect according to gender, as well as race/ethnicity, will be conducted. Binomial regression will be used evaluate if the difference between treatment groups in failure rate differs by subgroup. A model will be fit for

each factor of interest and will include the factor, treatment group, and an interaction term between the treatment group and the factor of interest.

Treatment effects in subgroups based on baseline factors will also be assessed. The subgroups of interest include baseline spherical equivalent anisometropia and baseline spherical equivalent refractive error. Failure status at 36 months post-randomization will be tabulated by subgroup and reviewed for consistency. The subgroup definitions for the planned subgroup analyses are as follows:

- Spherical equivalent anisometropia: <0.50D, 0.50D - <1.00D, 1.00D to 1.50D
- Spherical equivalent refractive error: +3.00D to <+4.00D, +4.00D to <+5.00D, 5.00D to 6.00D, $\geq 6.00D$

A Poisson regression using robust variance estimation will be used if the binomial regression model does not converge. If convergence issues are encountered when using the Poisson model, logistic regression will be used to make statistical inferences. For consistency, the same model will be used for all analyses. If the Poisson model is required for one of the analyses, the Poisson model will be used in all analyses.

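### The stereoacuity ANCOVA in SAP 3.5 adjusts for anisometropia measured after randomisation, an avoidable risk of bias because a baseline value exists

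*SAP*

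**What the plan says.** SAP 3.5 compares the arms on best stereoacuity, on a log scale, by analysis of covariance. Its covariates are fixed in one clause: "adjusting for age at the 36-month examination and the magnitude of anisometropia (using the most recent cycloplegic refraction"). Under SAP 3.0 the result counts as significant if p is below 0.01, separately in each age cohort.

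Four other places bear on this choice:

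- **SAP 2.2, item 2** judges changes in cycloplegic refraction at the 36-month assessment, so a refraction from that time normally exists.
- **SAP 4.3** will "compare the change in spherical equivalent (SE) refractive error in the eye that was more hyperopic at baseline from baseline to 36 months" between arms, then repeat this for the other eye. It plans a follow-up model: "If the change in refractive error differs at 36 months, an analysis of covariance model will be used".
- **SAP 3.7** names as subgroup factors "baseline spherical equivalent anisometropia and baseline spherical equivalent refractive error", so a baseline value of anisometropia is available.
- **SAP 3.2**, the parallel ANCOVA for distance acuity, takes its clinical covariate (acuity) from enrollment.

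The SAP gives no reason for using the latest refraction in 3.5 and plans no sensitivity analysis with the baseline value.

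**The concern.** A covariate measured after randomisation may itself be an effect of treatment. Adjusting for it removes whatever part of the treatment effect runs through it. If some unmeasured factor drives both anisometropia and stereoacuity, adjustment can also create a difference where none exists. The quantity of interest is the whole effect of prescribing glasses at once rather than on deterioration, and the adjusted difference may not be that quantity.

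SAP 4.3 treats refraction as an outcome that assignment may alter, while 3.5 conditions on a function of it. Section 4.3 analyses each eye separately and never the difference between eyes, so no planned analysis would tell a reader whether 3.5 is affected.

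The stake is limited to one secondary analysis per cohort. The primary Barnard's test is unadjusted, and so is the comparison in 3.6 ("A treatment group comparison of the proportion of subjects meeting age-normal near stereoacuity at 36 months will be performed"). Neither is affected.

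**Working it through.** The SAP gives no effect size, SD or sample size for this analysis, so there is no stated figure to reproduce. The check takes the algebra first, then a range of sizes.

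**1. The identity.** Let d be the change in mean anisometropia magnitude caused by assignment, and g the within-arm slope of log stereoacuity on that magnitude. Then

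adjusted difference = total effect − g × d, so bias = −g × d.

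There is no bias if d = 0 or g = 0. A non-zero g is presupposed by choosing anisometropia as a covariate.

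**2. How d can arise.** The covariate is an absolute value. Its mean moves if treatment affects the two eyes unequally. It can also move when mean effects are equal but change is more variable in one arm, because extra spread raises the mean of an absolute value. The baseline strata in 3.7 stop at 1.50 D ("Spherical equivalent anisometropia: <0.50D, 0.50D - <1.00D, 1.00D to 1.50D"), so differences between eyes are small enough for the order of the eyes to reverse.

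**3. Size. All inputs are assumptions, except that the cut at 1.50 D follows the top stratum in 3.7.** Baseline anisometropia is half-normal with SD 0.3 to 0.75 D, cut at 1.50 D. The SD of change in the between-eye difference is 0.25 to 0.5 D. The slope g is 0.1 to 0.4 log arcsec per D. The shift d was simulated with 2,000,000 children per setting. The bias range runs from lowest d × 0.1 to highest d × 0.4. The last column divides by log10(200/100) = 0.301.

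| Assumed effect of assignment | Size of d (D) | Size of bias (log arcsec) | Share of a 100-to-200 arcsec step |
|---|---|---|---|
| Between-eye difference 0.05 D | 0.016–0.041 | 0.002–0.016 | 0.5–5% |
| Between-eye difference 0.10 D | 0.027–0.083 | 0.003–0.033 | 1–11% |
| Between-eye difference 0.25 D (extreme) | 0.041–0.221 | 0.004–0.088 | 1–29% |
| Equal mean effects, extra SD 0.1–0.3 D in one arm | 0.005–0.081 | 0.0005–0.032 | 0.2–11% |

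For example, the top of the second row is 0.083 × 0.4 = 0.033, and 0.033 / 0.301 = 11%.

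**4. Confirmation by fitting the model.** ANCOVAs were fitted to 400,000 simulated children per setting, with slope 0.2 and with or without a shared cause of anisometropia and stereoacuity.

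- No shift: bias at most 0.0004 in size.
- Between-eye shift 0.10 D: bias −0.005 to −0.022.
- Extra spread of SD 0.3 D with no mean shift: bias −0.007 to −0.015.

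Every bias equalled −d × (fitted slope) within 0.001. The baseline-adjusted estimate matched the unadjusted randomised difference within 0.001.

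**5. A separate check with a simple additive shift.** With no direct effect, d = 0.2 D and g = 0.2, the true total effect is 0.2 × 0.2 = 0.04. The model with the 36-month covariate returned 0.00, and the baseline-adjusted model returned 0.039. With d = 0.2 D, a shared cause and no effect of assignment on stereoacuity, the 36-month covariate produced a spurious difference of about −0.026, against about 0 with the baseline covariate. A d of 0.2 D is reached in the table only in the extreme row, so these cases illustrate the mechanism and do not forecast this trial.

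**The case against.** The strongest reply is that nothing is shown to be wrong. Bias needs assignment to shift mean anisometropia, and the SAP has no evidence of that. Section 4.3 is exploratory and works eye by eye, and an equal change in both eyes of a child leaves the difference between them untouched. Planning for a difference is not evidence of one. **This stands**, and is why the point is put as a risk.

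The likely size is also small. Assuming a residual SD of 0.3 and 100 children per arm (neither is in the SAP), the standard error is 0.3 × √(2/100) = 0.042. The largest bias at 0.05 D is 0.016 / 0.042 ≈ 0.4 standard errors, which would move a 1% two-sided error rate to about 1.6%. The largest at 0.10 D moves it to about 3.7%. **This also stands** and keeps the point minor.

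The remedy can be challenged too. Version 1.0 of the SAP was written after study completion. Version 3.0 redefined best stereoacuity after "the leads realized that results reported for primary and secondary analyses were discordant". Changing the covariate now is one more results-aware change to the same endpoint, so one could keep the specified model in the lead and add the baseline model as the sensitivity analysis. The protocol is not to hand, and it may have fixed this covariate. **This stands in part.** Disclosure does not undo the timing, so the specified model must stay visible. It does not justify leading with the model that may miss part of the randomised effect.

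Finally, current anisometropia may predict stereoacuity better. That is a matter of precision and is costed under the fix. Age at the 36-month exam is also recorded late, but it is set by enrollment age and visit timing and carries no comparable risk.

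**Conclusion.** The concern holds, as a minor one. SAP 3.5 adjusts a randomised comparison for a value normally measured after randomisation, although a baseline value exists and the parallel acuity model uses an enrollment value. Whether bias occurs depends on whether assignment changes the mean magnitude of anisometropia, which the SAP does not reveal.

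Under the assumed ranges, modest between-eye effects (0.05 to 0.10 D) bias the difference by 0.002 to 0.033 log arcsec, and only an extreme 0.25 D approaches 0.09. These figures rest wholly on assumptions about the spread of anisometropia and its slope on stereoacuity. The algebra and the recovery of the full effect by baseline adjustment do not depend on them.

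**What to change.** 1. In SAP 3.5, take the magnitude of anisometropia from the baseline cycloplegic refraction, the same quantity that 3.7 already uses.
2. Report the model with the most recent refraction beside it, labelled as the model specified in version 3.0 and now a sensitivity analysis.
3. Tabulate the mean and SD of 36-month anisometropia magnitude by arm and cohort, so that readers can judge whether the bias can arise.
4. Record in the version history that the change followed review of results, and note any departure from the protocol if the protocol names this covariate.

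**Cost.** A few words, one rerun per cohort and a two-line table. Some precision may be lost. If current anisometropia correlates r with log stereoacuity and the baseline value carries a fraction k of that correlation, the standard error is multiplied by √[(1 − k²r²)/(1 − r²)]. With assumed r of 0.2 to 0.5 and k of 0.5 to 0.9:

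- r = 0.2, k = 0.9: √(0.9676/0.96) = 1.004
- r = 0.3, k = 0.7: √(0.9559/0.91) = 1.025
- r = 0.5, k = 0.5: √(0.9375/0.75) = 1.118

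The increase is therefore 0.4% to 12%. The other cost is a further post-results change to an endpoint already redefined in versions 2.0 and 3.0, which is why steps 2 and 4 belong with step 1.

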2.3 Additional Approaches to Primary Analyses

The primary treatment comparisons will be repeated in the following ways:

1. Include data only from subjects who complete the 36-month visit within the protocol window (34 to 38 months after randomization).
2. The primary analysis will be repeated, using only the initial assessments to identify failure at 3 years. If a change in refractive correction was necessary after formal failure criteria were met and confirmed by a retest, measurements reported for initial assessments performed with trial frames at the 37-month visit will replace measurements reported with trial frames at the 36-month visit if the assessment was failed.
3. The primary analysis will be repeated, imputing data for subjects with incomplete or no data at the primary outcome visit. Data will be imputed for subjects classified as “not failure” at 3 years who meet any of the following criteria: 1) the 36-month visit was not completed or was completed out of window, 2) a required 37-month visit was not completed, 3) an initial assessment or required retest was not performed and the available data indicates that the subject is a failure, or 4) no data was reported for an assessment, or an eye in the case of visual acuity. The imputation procedure is described in section 2.5.
4. The primary analysis will be repeated, adjusting for age at 36-month visit. Barnard’s Exact test does not allow for adjustment. Instead, binomial regression will be used to obtain the adjusted difference in failure rate between the treatment groups. If the model does not converge, Poisson regression using robust variance estimation will be used instead. If the Poisson model does not converge, logistic regression will be used to test the difference in treatment groups, controlling for age.
5. The distribution of the following baseline factors will be reviewed by treatment group: age, visual acuity, and stereoacuity. If factors appear to be confounders, defined as imbalance between treatment groups, binomial regression will be used to evaluate the treatment group difference in failure rates, controlling for all confounding factors. The characteristics will be categorized as follows:
 - a. Age: 1 to <2, 2 to <3, 3 to <4, 4 to <5, 5 to <6 years
 - b. Visual acuity: 20/20 or better, 20/25, 20/32, 20/40, 20/50
 - c. Stereoacuity: 40, 60, 100, 200, 400

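### The stereoacuity ANCOVA in SAP section 3.5 leaves out baseline stereoacuity, which gives up some precision in a secondary analysis but causes no bias

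*SAP*

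**What the plan says.** The secondary analysis of near stereoacuity is specified in section 3.5: "A treatment group comparison of best stereoacuity (log arcseconds) will be performed using an ANCOVA model". The covariates are two, "adjusting for age at the 36-month examination and the magnitude of anisometropia", with anisometropia taken from the latest cycloplegic refraction. No baseline value of stereoacuity enters the model.

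Section 3.2 sets up the corresponding ANCOVAs for distance acuity in the better-seeing and worse-seeing eye. There the baseline value of the outcome is included: "Both analyses will adjust for age at the 36-month exam and visual acuity in the eye at enrollment".

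Section 2.3 item 5 shows that the SAP treats stereoacuity as a baseline factor: "The distribution of the following baseline factors will be reviewed by treatment group: age, visual acuity, and stereoacuity". The categories are given as "Stereoacuity: 40, 60, 100, 200, 400". If imbalance is seen, the planned use is confined to the failure outcome: "binomial regression will be used to evaluate the treatment group difference in failure rates, controlling for all confounding factors".

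The threshold is in section 3.0: "Secondary analyses will be considered significant if the p-value is less than 0.01". The same section has the secondary analyses run separately in the two age cohorts and refers them to the principles of section 2.2.

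**The concern.** A baseline measurement of the outcome is the natural first covariate in an ANCOVA. The SAP follows that practice for acuity in section 3.2 and departs from it for stereoacuity in section 3.5, without giving a reason. By the SAP's own account in section 2.3 item 5, the variable is a baseline factor that takes several levels.

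What is at stake is efficiency. If baseline stereoacuity predicts 36-month stereoacuity beyond age and anisometropia, leaving it out gives a wider confidence interval for the treatment difference than the data could support. This matters somewhat more here because each cohort is analysed alone and the significance threshold is strict.

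**Working it through.** **Is there a figure to reproduce?** No. The SAP gives no sample size, standard deviation, power or baseline-to-outcome correlation for stereoacuity. The calculation below is therefore conditional on assumed values.

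**Inputs**
- Covariates in the planned model: age at the 36-month exam and anisometropia (section 3.5).
- Significance level: 0.01 (section 3.0). The SAP does not state sidedness for secondary analyses; two-sided is assumed.
- r: partial correlation of baseline with 36-month log stereoacuity, given age and anisometropia. Assumed at 0.2, 0.3 and 0.5.
- t: share of analysed children with a baseline value. Not given in the SAP; taken as 1 or 0.5.

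**Formulas**
- Residual variance factor when every child has a baseline value: 1 − r².
- With a missing-value indicator and share t tested: 1 − t·r². This assumes the same outcome variance in children with and without a baseline value.
- Confidence interval width factor: the square root of the variance factor.
- Equivalent gain in sample size: 1/(variance factor) − 1.

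**Results**

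| r | Variance factor, t = 1 | CI width factor, t = 1 | Equivalent extra children, t = 1 | Variance factor, t = 0.5 |
|---|---|---|---|---|
| 0.2 | 1 − 0.04 = 0.96 | 0.980 | 4.2% | 1 − 0.02 = 0.98 |
| 0.3 | 1 − 0.09 = 0.91 | 0.954 | 9.9% | 1 − 0.045 = 0.955 |
| 0.5 | 1 − 0.25 = 0.75 | 0.866 | 33.3% | 1 − 0.125 = 0.875 |

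At r = 0.5 the interval narrows by about 13% with complete baselines. With half of them missing, √0.875 = 0.935, so it narrows by about 6.5%. At r = 0.2 with complete baselines it narrows by about 2%.

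**Illustration in terms of power.** Take a hypothetical 94 children per arm, which gives 80.3% power for a difference of 0.5 SD at two-sided 0.01 without the baseline covariate. Adding it with complete baselines gives 82.2%, 84.6% or 91.7% power at r = 0.2, 0.3 or 0.5. Neither the 94 nor the 0.5 SD comes from the SAP.

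**Cost in degrees of freedom.** In the same illustration N = 188. The planned model has four parameters (intercept, treatment, age, anisometropia), leaving 184 residual degrees of freedom. One more covariate costs a variance factor of about 184/183 = 1.005; a covariate plus an indicator costs about 184/182 = 1.011. Both are smaller than the gain at r = 0.2 with complete baselines (0.96).

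**Does another provision already supply the adjustment?** Section 2.3 item 5 acts only on failure rates and only if imbalance appears. Section 2.2 item 6 allows factors that look imbalanced and are related to acuity, stereoacuity or strabismus into a model. It is framed as a complement to the primary analysis, and section 3.0 then points the secondary analyses to section 2.2. At most this opens a conditional route. It does not plan adjustment for baseline stereoacuity whatever the observed balance, and that is what would give the precision.

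**The case against.** The strongest reply is that this is a preference and not an error. Omitting a prognostic covariate from a randomised ANCOVA introduces no bias, and two analyses of different outcomes may have different covariates: section 3.5 includes anisometropia and section 3.2 does not. That is right as far as it goes. The difference between the sections is not a contradiction, and the point stands only as lost efficiency with no stated reason.

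Several stronger readings are tempting, and the SAP does not support them:

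- *That chance imbalance in baseline stereoacuity has no remedy in section 3.5.* Section 2.2 item 6, reached through section 3.0, can be read as admitting an imbalanced factor. The route is conditional and loosely worded, but it exists.
- *That baseline stereoacuity is known to be a strong predictor.* The SAP says nothing on this. If r is 0.2 or less, the gain is 4% of variance or less.
- *That baseline and outcome are the same measurement.* The outcome is the best of up to four readings (with and without trial frames, test and retest), with nil set to 1600. The baseline item appears only as five categories, with no correction state or best-of rule.
- *That the loss applies equally in both cohorts.* The SAP does not say which children had a baseline value. In children aged 12 to <36 months it may be missing for many or all.

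Anisometropia might be offered as a substitute. It is a different measure, and the latest refraction may post-date randomisation, so it is not a baseline value of the outcome.

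**Conclusion.** The point holds as a minor one. Section 3.5 omits a covariate that the SAP itself lists as a baseline factor and whose counterpart it uses in section 3.2. The treatment comparison stays valid and the primary analysis is unaffected. For r between 0.2 and 0.5, the precision forgone is 4% to 25% of residual variance with complete baselines, and 2% to 12.5% if half the children have one. These figures rest on an assumed r, on an assumed share tested and, for the partial case, on equal outcome variance in children with and without a baseline value. The direction is certain for any r large enough to repay one or two degrees of freedom; the size cannot be settled from the SAP. The case is reasonable for the 36 to <72 month cohort and unproven for the younger one.

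**What to change.** In section 3.5, for the 36 to <72 month cohort, add a model with baseline near stereoacuity (log arcseconds) as a further covariate. Include a missing-value indicator so that no analysed child is dropped. Whether a baseline value exists is settled before treatment starts, so the indicator does not bias the comparison. Leave the 12 to <36 month cohort on the planned model.

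The version history shows that version 1.0 was drafted after the study was completed and that version 3.0 followed review of results that the leads found discordant. The added model should therefore not replace the planned one. Report the two side by side and label the baseline-adjusted model post hoc.

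The cost is a sentence or two of SAP text, one extra model, and one degree of freedom, or two with the indicator. The two cohorts would also no longer have identical sets of models. The benefit may be small if r is low or few children have a baseline value.
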